Although we have assessed the proposed study as one of minimal risk, the potential exists for anticipated and/or unanticipated adverse events, serious or otherwise, to occur since it is not possible to predict with certainty the absolute risk in any given individual or in advance of first-hand experience with the proposed study methods. Therefore, we provide a plan for monitoring the data and safety of the proposed study as follows:

Adverse events will be monitored for each subject participating in the study and attributed to the study procedures / design by [name] according to the following categories:

- a.) Definite: Adverse event is clearly related to investigational agent/participation.
- b.) Probable: Adverse event is likely related to investigational agent/participation.
- c.) Possible: Adverse event may be related to investigational agent/participation.
- d.) Unlikely: Adverse event is likely not to be related to the investigational agent/participation.
- e.) Unrelated: Adverse event is clearly not related to investigational agent/participation.

The following scale will be used in grading the severity of adverse events noted during the study:

- 1 Mild adverse event
- 2 Moderate adverse event
- 3 Severe unanticipated adverse event resulting in inpatient hospitalization or prolongation of existing hospitalization, a persistent or significant disability/incapacity, or a congenital anomaly/birth defect;
- 4 Life threatening event or
- 5 Fatal adverse event.

In addition to grading the adverse event, [name] and the study team will determine whether the adverse event meets the criteria for a Serious Adverse Event (SAE). An adverse event is considered serious if it:

1. is life-threatening
2. results in in-patient hospitalization or prolongation of existing hospitalization
3. results in persistent or significant disability or incapacity
4. results in a congenital anomaly or birth defect OR
5. results in death
6. based upon appropriate medical judgment, may jeopardize the subject's health and may require medical or surgical intervention to prevent one of the other outcomes listed in this definition, or
7. adversely affects the risk/benefit ratio of the study.

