The study team, in consultation with the Yale TCORS Independent Data Safety Monitoring Board (DSMB), will evaluate the adverse event and determine whether the adverse event affects the Risk/Benefit ratio of the study and whether modifications to the protocol or consent form are needed. The DSMB includes experts in the field of tobacco use behaviors. The DSMB will review the study information and the plans for review prior to the initiation of the studies. They will provide an ongoing review every six months or more often if requested by the Board. The summary of the DSMB meeting will be submitted to the Yale HIC and to NIDA following each meeting.

Subjects will be closely monitored for safety throughout the research trial. Although in our experience this is a very rare event, subjects who show significant deterioration (e.g., increased substance use or psychiatric symptoms, including significant suicidal or homicidal ideation), will be withdrawn from the study and referred for appropriate treatment.

At any point if the investigator feels that subjects' health or well-being may be threatened by continuation in the study, subjects will be withdrawn from the study. If participants have a medical emergency, they will be instructed to call 911. Subjects who experience a significant psychiatric or medical problem that requires overnight hospitalization at an acute care facility will be considered to have experienced an SAE.

The Principal Investigator, [name], will report the following types of adverse events to the Yale University Human Investigation Committee (HIC):

- a) serious AND unanticipated AND possibly, probably or definitely related events;
- b) anticipated adverse events occurring with a greater frequency than expected; and
- c) other unanticipated problems involving risks to subjects or others.

These adverse events or unanticipated problems involving risks to subjects or others will be reported to the Yale HIC within 5 days of it becoming known to [name]. The procedures for SAE reporting include written documentation using the clinical notes related to the adverse event and specific forms detailing the event with a sign-off by all appropriate supervisory personnel.

Communication of recommendations and decisions from all parties (Yale Human Investigation Committee) will be made back to [name] in a timely manner.

- i. What provisions are in place for management of interim results?

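### Grade 3, the only severe grade on the adverse-event scale, also requires the event to be unanticipated and to have a listed outcome, so some severe events have no defined grade

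*Combined protocol and SAP*

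**What the plan says.** All the relevant text is in Section I, item 8 (Minimizing Risks).

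- **Purpose of the scale.** It is introduced with "The following scale will be used in grading the severity of adverse events noted during the study". It is thus a severity scale, meant for every adverse event.
- **Grades 1 and 2.** These are bare intensity terms; the second is simply "2 Moderate adverse event".
- **Grade 3.** It reads "3 Severe unanticipated adverse event resulting in inpatient hospitalization or prolongation of existing hospitalization, a persistent or significant disability/incapacity", followed by "or a congenital anomaly/birth defect".
- **Grades 4 and 5.** The fourth is "4 Life threatening event or" and the fifth is a fatal event. Neither depends on expectedness.
- **Seriousness.** This is decided in a further step, opened by "In addition to grading the adverse event", against a seven-item SAE list. Items 2 to 4 of that list are the same three outcomes that appear in grade 3.
- **Expectedness.** This enters through the criteria for reporting to the HIC. One criterion covers events that are serious, unanticipated and at least possibly related. Another covers "anticipated adverse events occurring with a greater frequency than expected".
- **What the protocol foresees.** The section opens by saying that "the potential exists for anticipated and/or unanticipated adverse events, serious or otherwise, to occur".

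**The concern.** Severity, seriousness and expectedness are three separate attributes of an adverse event, and the protocol has a place for each. Grade 3 merges them. Grades 1, 2, 4 and 5 can be assigned without asking whether the event was expected, but grade 3 cannot. Because it is the only severe grade, a severe event that misses either added condition has nowhere to go on the scale.

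What is at stake is whether the severity record is complete and consistent. Two raters who meet the same severe but anticipated event have no written rule telling them how to grade it. The added conditions also bring no new information, since both are assessed elsewhere in the same section.

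**Working it through.** The plan states no figure to reproduce here. The check is a reading of the grade definitions followed by a count of event types.

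**Step 1: conditions for grade 3.** As written, an event must be (a) severe, (b) unanticipated, and (c) result in at least one of: inpatient hospitalization or its prolongation; persistent or significant disability or incapacity; congenital anomaly or birth defect.

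**Step 2: event types.** Take severe events that are neither life-threatening nor fatal, since grades 4 and 5 take the rest. Cross expectedness (2 levels) with outcome (hospitalization, disability, congenital anomaly, none; 4 levels): 2 × 4 = 8 types.

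| Outcome | Unanticipated | Anticipated |
|---|---|---|
| Hospitalization or prolongation | Grade 3 | No grade |
| Disability or incapacity | Grade 3 | No grade |
| Congenital anomaly or birth defect | Grade 3 | No grade |
| None of the three | No grade | No grade |

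Grade 3 covers 3 types, leaving 8 − 3 = 5 without a grade. If the three outcomes are collapsed into present or absent, there are 2 × 2 = 4 types, of which 1 is covered. The two counts describe the same gap. Both depend on how the categories are drawn, and neither is a rate.

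**Step 3: does the protocol contemplate events in the gap?** Yes.

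- It expects anticipated as well as unanticipated events, including serious ones. An anticipated severe event leading to admission is an SAE under item 2 of the list and meets no severity grade.
- SAE item 6 (medical judgment that health may be jeopardized) and item 7 (adverse effect on the risk/benefit ratio) can make an event serious without any of grade 3's outcomes. A severe event that is serious only on those grounds has no grade, even if unanticipated.

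**Step 4: is a grade supplied elsewhere?** No. No other part of the document grades these events or gives a fallback rule.

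**Step 5: what depends on the grade?** SAE status is decided separately. HIC reporting turns on seriousness, expectedness, relatedness and frequency. Withdrawal of a subject rests on deterioration or the investigator's judgment. Section I, item 9 (Statistical Considerations) plans no analysis by grade.

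**The case against.** The strongest defence is that nothing in the protocol turns on the grade. This is a 30-person pilot that the protocol assesses as minimal risk, and the SAE and reporting steps work without it. That stands, and it is why the point is minor.

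A second defence is that the outcome wording only illustrates or defines what severe means. The text does not mark the outcomes as examples, although the same section marks examples elsewhere. Even on that reading, the requirement that the event be unanticipated remains, so anticipated severe events still have no grade.

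A reader might also infer more than the documents support:

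- *Any severe event managed without admission is ungraded.* Not so. An unanticipated severe event with disability or a congenital anomaly fits grade 3 without admission. Anticipated events that are life-threatening or fatal fit grades 4 and 5.
- *Such events will be recorded as moderate.* The protocol has no rule for them. Downgrading is one thing a rater might do, but it is not something the plan prescribes.
- *The principal investigator's monthly reviews and the six-monthly data safety monitoring board (DSMB) reviews will understate severe events.* The documents do not say that either receives tabulations by grade. The study team evaluates the event itself in consultation with the DSMB.
- *The gap covers the events most likely here, such as severe withdrawal.* The available text gives no event rates and no list of anticipated events. Participants keep smoking supplied cigarettes throughout, and withdrawal is measured separately with its own scale.

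**Conclusion.** The grade 3 definition is wrong as written, and the defect is minor. A severe event that is neither life-threatening nor fatal has no defined grade if it is anticipated or has none of the three listed outcomes. This rests on reading grade 3's words as conditions that must all hold, which is their plain sense.

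The consequence is limited to the severity record. A reader might infer that events would escape SAE or HIC reporting. The documents do not support that, because neither process uses the grade. The number of events affected in this trial cannot be estimated from the documents.

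**What to change.** Reword grade 3 as a severe adverse event, judged on intensity alone. Remove from the grade the requirement that the event be unanticipated, together with the hospitalization, disability and birth-defect outcomes. Leave seriousness to the SAE list that follows and expectedness to the HIC reporting criteria. Every adverse event can then be graded, and no information is lost.

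The cost is a one-line amendment. A few more events may be labelled grade 3. The SAE criteria, the HIC reporting triggers and the planned analyses are unchanged.

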Aim 1: Investigate whether switching to non-menthol cigarettes changes cigarette satisfaction and smoking behavior

Hypotheses: We expect that switching to a non-menthol cigarette will be less reinforcing and result in fewer cigarettes smoked per day, lower nicotine dependence, and greater quitting motivation/interest. Pilot data will be used to estimate effect sizes for these outcomes to inform the development of larger follow-up studies.

Aim 2: Evaluate the utility of objective smoking measures to assess behavior and adherence to the switching paradigm

Hypotheses: We expect that we will be able to quantify and verify self-reported smoking behavior with several objective measures of smoking behavior: collecting spent cigarette filters to measure number of cigarettes and quantify smoking intensity with filter weight and length, quantifying urine menthol glucuronide as a marker of menthol exposure.

2. **Background:** Describe the background information that led to the plan for this project. Provide references to support the expectation of obtaining useful scientific data.

Investigating menthol tobacco product use is critical for informing regulatory efforts. Although the Tobacco Control Act banned the sale of tobacco cigarettes with flavor additives, menthol flavor is currently exempt from this ban. While the overall rate of cigarette smoking has declined in recent years, the proportion of smokers using mentholated cigarettes has increased¹. Specifically, data from the National Survey on Drug Use and Health indicate the rate of past month menthol cigarette use increased from 7.7% in 2004 to 8.2% in 2010, while the rate of non-menthol cigarette use decreased from 17.1% to 14.6% during that time¹. Menthol additives are found in several nicotine containing products, including cigars, cigarillos, and e-cigarettes, although conventional cigarettes are still the most frequently used product by adult smokers². Menthol additives in tobacco pose a serious public health problem given evidence that smokers who use menthol cigarettes have greater risk of smoking-related morbidities³, and worse cessation outcomes^{4,5}. Additionally, use of menthol cigarettes is associated with higher rates of smoking and dependence^{6,7}. Research is

needed to better understand how menthol additives influence smoking behavior and enhance the addictive potential of tobacco products.

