Screening Assessments: To screen for eligibility, participants will complete several assessments: 1) Cigarette preference questions assess current use of menthol cigarettes (i.e., “what brand of cigarettes do you prefer?” “what brand of cigarettes do you normally smoke?”). 2) Smoking history to assess smoking quantity and frequency such as number of cigarettes per day and number of years smoked. 3) Expired breath carbon monoxide (CO) measured in parts per million to confirm smoking status. 4) Drug use: to confirm participants are not currently using other substances (other than caffeine or nicotine) assessments will include i) a time-line follow-back interview to assess self-reported drug use quantity and frequency, ii) urine drug toxicology screens, and iii) current blood alcohol level measured with a breathalyzer.

Visit Assessments: Eligible individuals will complete self-report assessments at baseline and research visits: 1) Nicotine dependence, measured by 1) Time to first cigarette in the morning as an index of smoking reinforcement^{9,10}, 2) Fagerstrom Test for Nicotine Dependence⁹ and Wisconsin Inventory of Smoking Dependence Motives^{11,12} to assess multiple dimensions of tobacco dependence such as automaticity, loss of control, and affective enhancement. Additional

assessments include: 3) Questionnaire on Smoking Urges-brief ¹³ to measure cigarette craving, 4) Wisconsin Smoking Withdrawal Scale ¹⁴, to assess 7 constructs of nicotine withdrawal: anger, anxiety, concentration, craving, hunger, sadness, and sleep and 5) Confidence and interest in quitting smoking, rated from 1 (not at all) to 10 (extremely) and 6) measures of smoking behavior and cigarette reinforcement and satisfaction.

Biological Measures: Biomarkers of cigarette and menthol exposure will be collected at baseline and weekly research visits (day 7, 14, 21) to examine changes from baseline and to corroborate self-reported tobacco product use and menthol exposure during the trial. 1) Expired breath carbon monoxide (CO) measured in parts per million, 2) Urine cotinine to quantify nicotine exposure, 3) Menthol glucuronide measured in the same urine sample as a marker of menthol exposure.

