Adherence: Adherence to use of the specified cigarettes in Phase I and II will be closely monitored via subjective and objective measures. Participants will report the total number of cigarettes consumed each day and will be instructed how to save and return spent cigarette filters so the count can be verified by research staff, a procedure that has been utilized previously to verify adherence ¹⁵. Biological measures will monitor menthol exposure and can be compared between Phase I and Phase II to quantify reductions in menthol exposure. We aim to restrict access to menthol cigarettes during Phase II by recruiting only smokers who do not currently live with menthol smokers, collecting any remaining mentholated cigarettes from participants before switching to non-menthol cigarettes, and providing free cigarettes to discourage substitution. Additionally, we will assess participants' use of other mentholated products (e.g., mint toothpaste or gum) or other extraneous tobacco products that are not a part of the study (e.g., e-cigarettes, other tobacco products) each week during the trial. This will allow us to estimate any compensatory menthol or tobacco product use during the switching phase of the study. Lastly, we will incentivize participant reporting by providing compensation for returning spent cigarette filters.

4. **Subject Population:** Provide a detailed description of the types of human subjects who will be recruited into this study.

We will recruit current adult (at least 18 years old) daily smokers who report smoking at least 5 cigarettes per day for at least the past 6 months. See detailed inclusion and exclusion criteria below.

5. **Subject classification:** Check off all classifications of subjects that will be specifically recruited for enrollment in the research project. Will subjects who may require additional safeguards or other considerations be enrolled in the study? If so, identify the population of subjects requiring special safeguards and provide a justification for their involvement.

 Children	 Healthy	 Fetal material, placenta, or dead fetus
 Non-English Speaking	 Prisoners	 Economically disadvantaged persons
 Decisionally Impaired	 Employees	 Pregnant women and/or fetuses

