The principal investigator is responsible for monitoring the data, assuring protocol compliance, and conducting the safety reviews at the specified frequency monthly. During the review process the principal investigator will evaluate whether the study should continue unchanged, require modification/amendment, or close to enrollment. The principal investigator and the Institutional Review Board (IRB) have the authority to stop or suspend the study or require modifications.

- ii. What will the multi-site process be for protocol modifications? N/A this is a single-site study

9. **Statistical Considerations:** Describe the statistical analyses that support the study design.

Data analyses will be conducted with SPSS software. Effect size estimates with 95% confidence intervals will be constructed for each aim to inform future studies. The primary statistical analyses will use within-person repeated measures to test for differences in smoking behavior (e.g., number of cigarettes per day, nicotine dependence) in menthol versus non-menthol phases.

Justification for sample size: Estimation of sample size (n=30) is based on achieving a clinically meaningful precision in effect size estimates for the primary outcome of interest. A power analysis based on $\alpha=.05$ and $\beta=.80$ suggests a sample size of 30 subjects is sufficiently powered to detect medium or large effects ($d>.50$) within-person. Although we will be unable to detect smaller effects, this sample size is reasonable for a pilot study, and data will be used to test the feasibility of the paradigm and adherence monitoring methodology and to estimate effect sizes to inform the optimal sample size for a larger follow-up study.

Data Monitoring: Procedures for data collection, data management, monitoring of data quality and data analysis have been developed and refined in our previous tobacco studies. An experienced data analyst and the PI will supervise these procedures which include use of a computerized database to monitor research activities, screening and enrollment, compliance with protocol, completion of scheduled assessments, and data retrieval. Data quality will be ensured by: 1) extensive training/supervision of research staff in data collection; 2) preliminary review of all assessment instruments prior to data entry and checks for completeness and coding errors; 3) double data entry of written assessment instruments; 4) error-checking statistical programs.

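### The sample-size paragraph gives β as .80, which is 20% power; with power of .80 intended, 30 complete pairs reach 80% at about d=.53 on the simplest reading, and the basis of the calculation is not stated

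*Combined protocol and SAP*

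**What the plan says.** The only power statement is in Section I, item 9 (Statistical Considerations), under the justification for sample size. It begins "A power analysis based on $\alpha=.05$ and $\beta=.80$ suggests a sample size of 30 subjects", and its claim is that the analysis "suggests a sample size of 30 subjects is sufficiently powered to detect medium or large effects", given there as within-person d>.50. The same paragraph opens with a precision rationale: "Estimation of sample size (n=30) is based on achieving a clinically meaningful precision in effect size estimates for the primary outcome of interest". It gives no interval width. It adds that smaller effects will not be detectable and that this is acceptable in a pilot.

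On the analysis, item 9 says: "The primary statistical analyses will use within-person repeated measures to test for differences in smoking behavior" between the menthol and non-menthol phases. It does not name the test used for the power calculation, its direction, the SD that standardises d, a within-person correlation, or the number of values per phase.

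Other sections bear on those gaps without filling them:

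- The Aim 1 hypotheses are directional. Switching is expected to "result in fewer cigarettes smoked per day, lower nicotine dependence, and greater quitting motivation/interest".
- The Research Plan schedules repeated measurement. Under Visit Assessments, "Eligible individuals will complete self-report assessments at baseline and research visits"; under Adherence, "Participants will report the total number of cigarettes consumed each day".
- Section III, item 1 sets the enrolment target at 30, the same number as in the power statement.

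**The concern.** There are two separate problems.

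The first is the symbol. β is the probability of missing a true effect, so β=.80 describes a study that misses four true effects in five. That cannot stand in the same sentence as a claim of sufficient power.

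The second appears once power of .80 is read in. The effect at which 30 participants give 80% power depends on the test direction, the standardiser and the number of values per phase. As none is stated, the d>.50 threshold cannot be checked, and on the simplest reading it falls a little short.

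Little is at stake in this pilot itself. But its declared purpose includes informing the sample size of a larger study, and a mislabelled error rate with no stated basis is a poor starting point for that.

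**Working it through.** **Inputs from the protocol (Section I, item 9):** α=.05; β printed as .80; n=30; within-person d>.50.

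**Assumed, because the protocol is silent:** two-sided test; one value per phase; d = mean within-person difference ÷ SD of those differences; 30 complete pairs. Within-person correlations r are also assumptions where used below.

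**Method:** paired t-test. Power is the probability that a noncentral t with n−1 degrees of freedom and noncentrality d√n exceeds the critical value in absolute size.

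**Step 1: β as printed.** Power = 1 − .80 = .20. At d=.50 two-sided, 7 pairs give 20% power. With 30 pairs, 20% power is reached at d=.21. Neither leads to n=30 at d=.50.

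**Step 2: trying to reproduce n=30 with power .80.** The normal approximation gives n = ((1.960 + 0.842)/.50)² = 31.4. At n=30 its power is Φ(.50×√30 − 1.960) = Φ(0.779) = 78.2%, and 80% is reached at d = 2.802/√30 = .51. This comes close to the plan's figure and supports reading .80 as power.

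**Step 3: paired t, 30 pairs, two-sided.** Noncentrality at d=.50 is .50×√30 = 2.739; the critical t on 29 df is 2.045.

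| d | Power |
|---|---|
| .50 | 75.4% |
| .51 | 77.0% |
| .52 | 78.6% |
| .53 | 80.1% |
| .60 | 88.8% |

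Power reaches 80% at d=.529. At d=.50, 33 pairs give 79.5%, so 34 would be needed for 80%.

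**Step 4: bases that would meet the claim.**

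- *One-sided α=.05:* 84.8% at d=.50.
- *d on the raw-SD scale, one value per phase:* the effect on the difference scale is .50/√(2(1−r)). Power is 67.6%, 75.4% and 84.1% at r=.40, .50 and .60, and reaches 80% at r=.554.
- *Raw-SD d, one menthol visit against the mean of two non-menthol visits, equal correlations:* the effect is .50/√(1.5(1−r)). Power is 79.7% at r=.40 and 86.3% at r=.50, and reaches 80% at r=.405.

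**The case against.** The strongest reply is that only the β label is demonstrably wrong. The 75% and .53 figures depend on four choices that the protocol does not make, and Step 4 shows reasonable choices that clear 80%. Directional hypotheses could be taken to suggest a one-sided test, and repeated measurements are planned. The text also says d above .50, not equal to it, and .529 is only about .03 SD higher. Finally, n=30 is said to rest on precision, and missing smaller effects is openly accepted.

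Most of this stands. The shortfall is conditional and small. It does not vanish because the inequality is strict, since power at d=.51 and .52 is also below 80% on that reading. Directional hypotheses do not by themselves establish a one-sided test. Without a stated basis, the reader cannot tell which figure applies.

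One apparent rescue fails. A repeated-measures F test with three measurements and a conventional medium f=.25 needs only 28 subjects at r=.50. But a phase shift of raw-SD d=.50 over one menthol and two non-menthol values gives f = .50×√2/3 = .236. With noncentrality f²×30×3/(1−.50) = 10.0 on 2 and 58 df, power at n=30 is 79.4%. That generic figure therefore does not support the d=.50 claim.

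A reader might also infer that the study was really planned at 20% power, or that 30 is too few and 34 are required. The documents support neither. The wording of the claim and Step 2 both point to power of .80, and the 34 holds only under the assumptions of Step 3.

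**Conclusion.** The β value is wrong as written: it states 20% power, contradicts its own sentence and does not produce n=30. This part needs no assumption about the test.

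The optimistic threshold is the result on the simplest reading and not a proven error. With a two-sided paired t, one value per phase, d on the SD of differences and 30 complete pairs, the miss rate at d=.50 is about 25% instead of 20%, and 80% power starts at d=.53 instead of just above .50. Other bases meet the claim, but the plan does not state them.

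Severity is minor. This is a correction to a stated figure, not a fault in the design.

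**What to change.** Keep n=30. In the sample-size paragraph of Section I, item 9:

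1. Replace the β value with power=.80 (β=.20).
2. Restate the detectable effect to match the planned test. For a two-sided paired comparison, suitable wording is: *With two-sided α=.05 and power=.80 (β=.20), 30 complete pairs detect d≥.53, where d is the mean within-person phase difference divided by the SD of those differences; power at d=.50 is about 75%.*
3. If the calculation used another direction, standardiser or number of measurements per phase, state that basis, including any assumed within-person correlation, and give its matching figure instead.

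The cost is one sentence of protocol wording, with no change to sample size, design or analysis.
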